## 9.2 SAMPLE SIZE DETERMINATION

### Sample Size calculations

The primary goal of this aim is to test the efficacy of immersive VR in improving perceived pain. The trial will be a success if there is statistical evidence that either immersive VR group is better than control or sham VR. Preliminary studies showed that the PROMIS pain interference scale has a SD of 10. Assuming that the SD at baseline ( $SD_0$ ) and at 30 days ( $SD_1$ ) are similar and equal to 10 for this population, the variance for the difference in PROMIS from baseline to 30 days after intervention is  $Var_{diff} = SD_0^2 + SD_1^2 - 2\rho SD_0 SD_1$ , where  $\rho$  is the correlation coefficient between measurements at baseline and 30 days. A conservative estimate of this variance is achieved when  $\rho = 0$ . Therefore, the estimate  $SD_{diff} = (10^2 + 10^2)^{0.5} = 14.14$ . Let  $m_c$ ,  $mv_1$ , and  $mv_2$  be the mean change in PROMIS score from baseline to 30 days for the control, VR1, and VR2 groups, respectively.

We estimate power by simulating 10000 trial replicates and testing the null hypothesis that  $H_0: m_c = mv_1 = mv_2$  versus the alternative hypothesis that  $H_1: m_c \neq mv_1$  or  $m_c \neq mv_2$ . To maintain the familywise error rate at 0.05, a two-sample t-test is used to compare the control arm to each VR arm and the test is declared statistically significant if the p-value of the two-sided test is less than 0.025. Under the alternative hypothesis that  $|m_c - mv_1| = |m_c - mv_2| = 5$ , data from 120 patients in each of the three arms achieve 83% power to detect a clinically meaningful effect 5 units in the PROMIS score. The actual type I error rate is 0.049. For the secondary outcome of comparison between the two VR arms, we test the null hypothesis that  $H_0: mv_1 = mv_2$  versus the alternative hypothesis that  $H_1: mv_1 \neq mv_2$  at the two-sided 0.05 level of significance if there is statistical evidence that both VR arms are better than control. Using the same assumptions as above and simulating 10000 trial replicates, then if both VR arms are better than the control arm, we can achieve 71.4% power to detect 5 units in PROMIS score between the two VR arms. This power was derived under the alternative hypothesis  $|m_c - mv_1| = 5$  and  $|mv_1 - mv_2| = 5$ . The actual type I error rate for this conditional test is 0.02.

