### 9 STATISTICAL CONSIDERATIONS

#### 9.1 STATISTICAL HYPOTHESES

- **Primary Efficacy Endpoint(s):**

Primary Outcome: Pain interference over time as measured by PROMIS-Pain Interference 8a (T-Scored, Continuous).

Hypothesis: Immersive VR (Skills-based VR or Distraction VR) will lead to a greater improvement in pain interference than Sham VR over 30-day period.

Comparisons: Superiority for both of the following (1) Distraction VR therapy vs. sham VR therapy; (2) skills-based VR therapy vs. sham VR therapy.

Additional comparison: If there is a statistically significant difference in Skills based VR vs Sham VR, then a third test will be completed (3) Skills-based VR therapy vs Distraction VR therapy.

- **Secondary Efficacy Endpoint(s):**

Secondary Outcome: Pain interference over time as measured by PROMIS-Pain Interference 8a (T-Scored, Continuous).

Hypothesis: Immersive VR (Skills-based VR or Distraction VR) will lead to a greater improvement in pain interference than Sham VR at Day 60 and Day 90.

Comparisons: Superiority for both of the following (1) Distraction VR therapy vs. sham VR therapy; (2) skills-based VR therapy vs. sham VR therapy.

Additional comparison: If there is a statistically significant difference in Skills based VR vs Sham VR then a third test will be completed (3) Skills-based VR therapy vs Distraction VR therapy.

Secondary Outcome: Pain catastrophizing over time as measured by Pain Catastrophizing scale (PCS) short form.

Hypothesis: Skills-based VR will lead to a greater improvement in Pain catastrophizing than distraction-based VR or Sham VR.

Comparisons: Superiority for both of the following (1) Distraction VR therapy vs. sham VR therapy; (2) skills-based VR therapy vs. sham VR therapy, if there is a statistically significant difference in Skills based VR vs Sham VR then a third test will be completed (3) Skills-based VR therapy vs Distraction VR therapy

Secondary Outcome: Anxiety over time as measured by PROMIS Anxiety.

Hypothesis: Skills-based VR will lead to a greater improvement in PROMIS Anxiety than distraction based VR or Sham VR.

Comparisons: Superiority for both of the following (1) Distraction VR therapy vs. sham VR therapy; (2) skills-based VR therapy vs. sham VR therapy, if there is a statistically significant difference in Skills based VR vs Sham VR then a third test will be completed (3) Skills-based VR therapy vs Distraction VR therapy

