Secondary Outcome: Quality of sleep over time as measured by PROMIS Sleep Disturbance.

Hypothesis: Skills-based VR will lead to a greater improvement in sleep quality than distraction based VR or Sham VR.

Comparisons: Superiority for both of the following (1) Distraction VR therapy vs. sham VR therapy; (2) skills-based VR therapy vs. sham VR therapy, if there is a statistically significant difference in Skills based VR vs Sham VR then a third test will be completed (3) Skills-based VR therapy vs Distraction VR therapy

Secondary Outcome: Comparing the change from study baseline to Day 90 in weekly MME of prescribed medication.

Question: Which intervention is more effective in reducing opioid prescriptions of Morphine Milligram Equivalents (MME) or greater?

Hypothesis: We believe that Skills-based VR will have a statistically significant decrease in opioid use in comparison to distraction-based VR and Sham VR.

Comparisons: Superiority for both of the following (1) Distraction VR therapy vs. sham VR therapy; (2) skills-based VR therapy vs. sham VR therapy, if there is a statistically significant difference in Skills based VR vs Sham VR then a third test will be completed (3) Skills-based VR therapy vs Distraction VR therapy

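### The Day 30 Skills-versus-Distraction test has two different entry rules, and no section of the protocol or SAP says which one applies

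*Protocol*

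**What the plan says.** Protocol 9.1, under the primary endpoint, introduces the two sham comparisons with "Superiority for both of the following" and then adds: "If there is a statistically significant difference in Skills based VR vs Sham VR, then a third test will be completed", the third test being Skills against Distraction. Nothing is required of Distraction against Sham. The same rule follows each secondary endpoint, for example "if there is a statistically significant difference in Skills based VR vs Sham VR then a third test will be completed".

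Protocol 9.2 opens its account of the contrast with "For the secondary outcome of comparison between the two VR arms" and tests it at two-sided 0.05 only "if there is statistical evidence that both VR arms are better than control". SAP 3.5 and 3.5.1 repeat that rule. The outcome is the 30-day change in PROMIS score, so this is the same comparison on the same endpoint. Of its power the protocol says: "then if both VR arms are better than the control arm, we can achieve 71.4% power to detect 5 units in PROMIS score". It gives 0.02 as the type I error of the conditional test.

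For each sham comparison, Protocol 9.2 and SAP 3.5 say "the test is declared statistically significant if the p-value of the two-sided test is less than 0.025". Protocol 9.4.2 and SAP 4.6.1 state a two-sided 5% level and write out only the two sham hypotheses. SAP 6.3 promises sequential gatekeeping and closed testing over primary and secondary endpoints, but names no families, no order and no rule for this contrast.

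**The concern.** Protocol 4.2 gives the comparison of skills-based with distraction-based VR as a reason for having three arms. The two rules part company in one situation: Skills significant against Sham, Distraction not. An analyst following Protocol 9.1 would then run the contrast. An analyst following the SAP would not, because SAP 3.5 and 3.5.1 are the only places in the SAP that say when it is tested. A rule settled after that pattern has been seen would be open to challenge whichever way it went. The published power and error figures also describe only one of the two rules.

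**Working it through.** **Inputs.** 120 per arm (Protocol 9.2, SAP 3.3). SD 10 at baseline and at Day 30 with correlation 0, so the SD of change is √(10² + 10² − 0) = 14.14. Sham comparisons at two-sided 0.025, contrast at two-sided 0.05 (Protocol 9.2, SAP 3.5). No dropout. Effects below are Skills/Distraction points better than sham.

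**Method.** Two-sample t-tests on 238 df, 2,000,000 simulated trials per scenario. Write S for Skills better than Sham at 0.025, D for Distraction better than Sham at 0.025, and T for rejection of Skills against Distraction at 0.05. The Skills-only rule (9.1) runs the contrast on S. The both-arms rule (9.2, SAP) runs it on S and D. They disagree when S occurs without D.

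**Hand check.** The standard error of a difference is 14.14 × √(2/120) = 1.826, and 5/1.826 = 2.74. Power for 5 points is about 69% at 0.025 and 78% at 0.05.

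**The plan's own figures.**
- S or D at 5/5: 83.2% (stated 83%).
- T given S and D at 10/5: 71.0% (stated 71.4%).
- T given S and D at 5/5: 0.021 (stated 0.02).

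All three reproduce. Under the Skills-only rule the last two become 77.9% and 0.044, so the stated pair belongs to the both-arms rule.

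**How often the rules disagree.** The last column uses SD 10. That is an assumption: with SD 10 at both times, the SD after adjusting for baseline is 10√(1 − ρ²), at most 10.

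| Skills/Distraction | Skills-only opens | Both-arms opens | Disagree, SD 14.14 | Disagree, SD 10 |
|---|---|---|---|---|
| 5/5 | 68.6% | 53.9% | 14.7% | 4% |
| 10/5 | 99.9% | 68.5% | 31.4% | 5% |
| 5/0 | 68.6% | 1.2% | 67.3% | 93% |
| 5/10 | 68.5% | 68.5% | 0.0% | 0% |

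Last digits carry simulation error. At 0/5 (only Distraction works) each rule opens in about 1% of trials.

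**Power of the contrast, SD 14.14.** Conditional means given that the rule opens. Overall means that it opens and the contrast rejects.

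| Skills/Distraction | Skills-only, conditional | Skills-only, overall | Both-arms, conditional | Both-arms, overall |
|---|---|---|---|---|
| 10/5 | 78% | 78% | 71% | 49% |
| 5/10 | 71% | 49% | 71% | 49% |
| 5/0 | 87% | 59% | – | under 1% |

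**Error over the three Day 30 tests, Skills-only rule.** If all arms are equal, the contrast can reject only when Skills against Sham has already rejected, so the error is at most 2 × 0.025 = 0.05 (simulated 0.047). If the VR arms are equal and both better than sham, the contrast is the only true null and is tested at 0.05 (simulated 0.030 at 5/5, 0.050 at 10/10). The both-arms rule is stricter, so the same bounds hold. If each sham test is run at 0.05, as a literal reading of Protocol 9.4.2 and SAP 4.6.1 allows, the two alone give about 9.1% when all arms are equal.

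**The case against.** The both-arms wording sits in sample-size sections, and one could say that it only sets up a power calculation. But it is phrased as a rule for when the hypothesis is tested, and the SAP has no other.

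Trial success depends only on either VR arm against sham, so neither rule can change the primary conclusion. That stands. It also stands that 67% is the worst of the four cases. At the alternative that powers the primary comparison (both arms 5 better) the figure is 15%, and if Distraction is the better arm by 5 it is zero. The SD of 14.14 is conservative, as the protocol says ("A conservative estimate of this variance is achieved when"), because the planned model adjusts for baseline. A smaller SD shrinks the disagreement when both arms work and raises it when only Skills does.

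Three stronger readings are tempting, and the documents do not support them.
- A reader might infer that the Skills-only rule inflates type I error. With sham tests at 0.025 it does not, within the three Day 30 tests.
- A reader might infer that 71.4% and 0.02 are miscalculated. They reproduce, and both are presented as conditional.
- A reader might infer that the rules also differ in direction, since 9.1 speaks of a significant difference and 9.2 of being better than control. But 9.1 frames the sham comparisons as superiority, so both mean better than sham.

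Nor is the label a clear conflict: an additional comparison in 9.1 can also be a secondary outcome in 9.2. What is missing is its place in SAP 6.3.

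**Conclusion.** The contradiction holds for Day 30 PROMIS Pain Interference, and nothing in Protocol 9.4.2, SAP 4.6.1 or SAP 6.3 resolves it. The closed-testing sentence in SAP 6.3 does not help: a closed test of the three pairwise hypotheses needs only the global null and the pairwise test rejected, which is neither rule. The documents give opposite instructions in 0% to 67% of trials at SD 14.14, and 0% to 93% at an assumed SD of 10, depending on which arms work. These figures assume 120 analysed per arm and sham tests at 0.025. With sham tests at 0.05 and SD 14.14 the disagreement is 12% at 5/5, 22% at 10/5 and 75% at 5/0. The defect is an undefined testing rule, with power quoted for one version of it, on a comparison that the design names as a purpose. It is not a threat to the primary comparisons.

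**What to change.** Before unblinding, by a dated amendment that records blinded status:

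1. Choose one rule and write it identically in Protocol 9.1, 9.2 and 9.4.2 and SAP 3.5, 3.5.1, 4.6.1 and 6.3. Add the third hypothesis to Protocol 9.4.2 and SAP 4.6.1. Either rule is defensible; the Skills-only rule also allows the contrast when only Skills works.
2. In Protocol 9.4.2 and SAP 4.6.1, replace the 5% level for the sham comparisons with 0.025 each, as in the sample-size sections. The error control of the sequence depends on it.
3. In SAP 6.3, place the contrast in the sequence. Testing it at 0.05 protects only the three Day 30 tests: if the VR arms work equally well it can use the whole 0.05. Either make the secondary tests in the controlled family depend on earlier rejections so that the total stays at 0.05, or declare the contrast outside that family.
4. If the Skills-only rule is chosen, restate power with its basis labelled, as in the second table, with arm means and SD. If the both-arms rule is chosen, 71.4% and 0.02 can stay, labelled conditional, and 9.1 must change.

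The cost is one amendment to each document, with no new patients or data. It comes late, since Protocol 8.1 ends randomization on 9/5/2023, so the record of blinding matters. Under either rule the contrast is almost never tested if only Distraction works (about 1% of trials).

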### Power Estimation

We estimate power to assess the effect of VR type on treatment response using logistic regression, accounting for all possible confounding factors as described in Aim 1. The outcome variable in treatment response (binary) and the predictor of interest is VR type, traditional versus enhanced. Table 1 gives the minimum odds ratio that can be detected with 80% power with the two-sided 0.05 level of significance as a function of baseline probability of positive response when a patient is treated with traditional VR and  $R^2$ , the proportion of variability in the predictor of interest (VR type) that is explained by all relevant baseline covariates in the model using data from 120 patients in the traditional VR arm and 120 in the enhanced VR arm. For example, data from 240 patients achieve 80% power to detect an odds ratio of 2.19 if the probability of positive response when a patient is treated with traditional VR is 0.3 and 10% of the variability in VR type is explained by all other baseline covariates in the model. These odds ratios vary between 2.01 and 2.8 and are clinically meaningful. Therefore, we have enough power to test statistical significance of predictors of interest in the multivariable logistic regression model.

**Table 1.** Minimum detectable odds ratio as a function of the proportion of variability in VR type variable that is explained by all other relevant covariates in the model and the baseline probability of positive treatment response.

Baseline probability	R 			
	0.0	0.1	0.2	0.4
0.2	2.26	2.36	2.48	2.82
0.3	2.11	2.19	2.30	2.61
0.5	2.01	2.18	2.30	2.64

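### The smallest detectable odds ratio in Table 1 (2.01 at baseline probability 0.5, R² = 0) should be about 2.10, and the quoted range repeats the error

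*Protocol*

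**What the plan says.** Protocol 9.2, under Power Estimation, leaves the primary endpoint and turns to a binary treatment response compared between the two immersive VR arms: "We estimate power to assess the effect of VR type on treatment response using logistic regression". The operating conditions are given in full. On power and level: "Table 1 gives the minimum odds ratio that can be detected with 80% power with the two-sided 0.05 level of significance". On sample size: "using data from 120 patients in the traditional VR arm and 120 in the enhanced VR arm". The table has two margins. The rows are the "baseline probability of positive response when a patient is treated with traditional VR", set at 0.2, 0.3 and 0.5. The columns are R², described as "the proportion of variability in the predictor of interest (VR type) that is explained by all relevant baseline covariates in the model", set at 0.0, 0.1, 0.2 and 0.4.

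One cell is worked in the text, for baseline probability 0.3 and R² = 0.1: "data from 240 patients achieve 80% power to detect an odds ratio of 2.19". The paragraph then summarises the table, "These odds ratios vary between 2.01 and 2.8 and are clinically meaningful", and concludes that power is sufficient for testing predictors in the multivariable logistic model.

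SAP 3.5.1 repeats the table, the summary sentence and the conclusion. It differs only in calling the arms Distraction and Skills-based instead of traditional and enhanced.

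**The concern.** In the row for baseline probability 0.5 the entries are 2.01, 2.18, 2.30 and 2.64. The first step is out of pattern. From R² = 0 to R² = 0.1 the detectable odds ratio rises by 0.10 in the 0.2 row (2.26 to 2.36) and by 0.08 in the 0.3 row (2.11 to 2.19), but by 0.17 in the 0.5 row. R² acts only by shrinking the effective sample size, so there is no reason for one row to react twice as strongly as the others.

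The cell is the most favourable figure in the table and is carried into the sentence that supports the claim of adequate power. If it is wrong, both documents state a detectable effect that 120 patients per arm do not deliver at 80% power, and a later report could repeat it.

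**Working it through.** **Inputs**, all from protocol 9.2 (Power Estimation) and repeated in SAP 3.5.1: n = 120 per arm (N = 240, 1:1), power 0.80, two-sided α = 0.05, binary predictor, baseline probability p₁ = 0.2, 0.3 or 0.5, R² = 0.0, 0.1, 0.2 or 0.4.

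**Formula.** Neither document names one. The usual choice for a binary predictor at 1:1 uses the pooled variance under the null and the unpooled variance under the alternative, with the sample size multiplied by (1 − R²):

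- p₂ = OR·p₁ / (1 − p₁ + OR·p₁), p̄ = (p₁ + p₂)/2
- n(1 − R²) = [1.960·√(2p̄(1 − p̄)) + 0.8416·√(p₁(1 − p₁) + p₂(1 − p₂))]² / (p₂ − p₁)²

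**Step 1: reproduce the table.** Solving for the odds ratio at n = 120, computed value first and printed value in brackets:

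| Baseline probability | R² = 0.0 | 0.1 | 0.2 | 0.4 |
|---|---|---|---|---|
| 0.2 | 2.267 (2.26) | 2.362 (2.36) | 2.479 (2.48) | 2.821 (2.82) |
| 0.3 | 2.114 (2.11) | 2.199 (2.19) | 2.303 (2.30) | 2.611 (2.61) |
| 0.5 | **2.097 (2.01)** | 2.187 (2.18) | 2.300 (2.30) | 2.644 (2.64) |

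Eleven of the twelve cells agree within 0.01, including the worked example of 2.19. At those eleven printed odds ratios the power is 79.6% to 80.0%. One cell fails, by about 0.09.

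**Step 2: power at the printed 2.01** (p₁ = 0.5, R² = 0).

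- p₂ = 2.01/3.01 = 0.6678, so the difference is 0.1678 and p̄ = 0.5839
- √(2 × 0.5839 × 0.4161) = 0.6971
- √(0.25 + 0.6678 × 0.3322) = 0.6869
- z = (0.1678 × √120 − 1.960 × 0.6971)/0.6869 = (1.838 − 1.366)/0.6869 = 0.687
- Power = Φ(0.687) = 75.4%

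Sample size for 80% power at 2.01: [1.960 × 0.6971 + 0.8416 × 0.6869]²/0.1678² ≈ 134.3 per arm, or 268.6 in total. That is 268.6/240 = 1.12 times the number planned.

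**Step 3: power at 2.10.** p₂ = 2.10/3.10 = 0.6774, difference 0.1774, z = (1.944 − 1.364)/0.6845 = 0.847, power 80.1%. At 2.09 it is 79.7%.

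**Step 4: a check that does not depend on the formula in step 1.** If R² only reduces the effective sample size, ln(OR) scales approximately as 1/√(1 − R²). Scaling the 0.5 row back to R² = 0:

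- exp(ln 2.18 × √0.9) = 2.09
- exp(ln 2.30 × √0.8) = 2.11
- exp(ln 2.64 × √0.6) = 2.12

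The same scaling gives 2.23 to 2.26 in the 0.2 row (printed 2.26) and 2.10 to 2.11 in the 0.3 row (printed 2.11), so the approximation is good enough to show that 2.01 does not belong to its row.

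**Step 5: other methods.** Two-sided alternatives for a binary predictor (unpooled, Wald on the log odds ratio, arcsine, continuity-corrected and others) give 2.06 to 2.18 for this cell. Reading 0.5 as the overall response rate gives 2.07. One-sided versions give 1.90 to 1.99, and the formula for a continuous covariate gives 1.44 (two-sided) or 1.38 (one-sided); both groups miss the rest of the table. None gives 2.01 while matching the other cells.

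**The case against.** The strongest reply is that nothing turns on this cell. The sample size of 360 comes from the PROMIS Pain Interference simulation in protocol 9.2 and SAP 3.5. Table 1 describes what 120 per arm can detect and does not set that number. The primary analysis is a mixed model on a continuous score. The plan already accepts odds ratios up to 2.8 as clinically meaningful, so moving the favourable end from 2.01 to 2.10 leaves its conclusion intact. All of that stands, and it keeps the point minor.

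The method is also inferred, because neither document names it. That is true, but the inference rests on eleven matching cells, and step 4 needs only the row's own entries.

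Some printed values look truncated rather than rounded (2.267 as 2.26, 2.187 as 2.18), so the intended entry could have been 2.09. That is a fair limit on the second decimal. For the same reason, swapped digits are a plausible cause but not one the documents show. The upper end of 2.8 is simply 2.82 rounded and is not an error.

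It can be argued that R² = 0 matters least, because the model adjusts for covariates. This is weaker than it looks. VR type is randomised, so baseline covariates should explain little of it, and the columns near R² = 0 are the ones randomisation should bring about.

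**Conclusion.** The concern holds. For baseline probability 0.5 and R² = 0, the smallest odds ratio detectable with 80% power is about 2.10, not 2.01, and the lower end of the range in both documents is wrong for the same reason. At 2.01 the power is 75.4%, a shortfall of 4.6 percentage points, equivalent to about 29 more patients on 240.

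The value 2.10 assumes the standard two-sided formula for a binary predictor, which fits the rest of the table. That 2.01 is out of line with its own row does not depend on that choice. It is not a fault of text extraction, since the running text of both documents uses 2.01 as well. The correction is minor: the trial's sample size does not change, and the statement that power is adequate for this comparison probably survives.

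**What to change.** Rerun the calculation for the 0.5 row and name the formula or software beside the table. Change the first entry of that row from 2.01 to 2.10 (2.09 if the sponsor's convention is to truncate). Restate the range as 2.10 to 2.82, with both ends to two decimals. The lower end then remains the same cell, just below the 2.11 in the 0.3 row. Make the change in protocol 9.2 and in SAP 3.5.1, in the table and in the sentence.

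The cost is an edit to one cell and one sentence in each document and a slightly less favourable figure. Design, conduct and analysis are unaffected.

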#### 9.4.7 SUB-GROUP ANALYSES

Subgroup analyses are planned for the change from baseline in PROMIS-PI. An MMRM model will be used to test for treatment by subgroup interactions. Interactions with a significance level of less than 10% will be considered potentially important and flagged for further assessment. In general, the models will include fixed categorical effects for treatment, week, treatment by week interaction, subgroup, and treatment by subgroup interaction. The p-values of interaction terms will be presented, as well as the least squares means and 95% confidence intervals by treatment and subgroup classification factor. Descriptive statistics of the observed and change from baseline PROMIS-PI t-score will also be presented by treatment and week within each subgroup.

Subgroup analyses will be performed for the following subgroups:

- Dosage of VR (minutes per week)
- Previous experience with VR
- ITQ score
- Presence score
- Patient comorbidities
- History of spinal surgery
- Pain severity and duration
- Sociodemographics (i.e. age, sex, race, ethnicity, workers comp, marital status, education)
- Other treatments (see section 6.5)
- TAPS-1, TAPS-2
- Mood disturbances (e.g., current depressive disorder or not, severely depressed mood vs. non-depressed, etc.)
- Radicular vs. non-radicular back pain
- SSQ Cutoff (Score of >15)
- Treatment Expectation Question
- Perception of arm of study question
- Motion Sickness Propensity Survey

The primary MMRM models will be re-fit to include terms describing subgroups. The change from baseline PROMIS-PI score obtained at Day 30 will be compared between the treatment groups using MMRM analysis. The repeated measures are the change from baseline PROMIS-PI score obtained for Day 7, 15, 21, and 30, respectively. The model will include fixed categorical effects for treatment, week, treatment by week interaction, relevant subgroup, treatment by subgroup interaction, and the baseline PROMIS-PI score as a continuous covariate. The estimated least squares means and 95% confidence intervals on the treatment comparison for Day 7, 15, 21, and 30, will be presented in forest plots for each subgroup of relevance.

See Section 9.4.9 under exploratory analysis for more detail.

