#### 3.5.1 Power Estimation

For the primary endpoint of the study, there is 83% power to detect a clinically meaningful effect size of 5 units in PROMIS score between control and either VR arms at the 0.05 level of significance. This requires 360 patients randomized on a 1:1:1 ratio.

For one of the secondary endpoints of comparison between the two VR arms, we test the null hypothesis that  $H_0: mv1 = mv2$  versus the alternative hypothesis that  $H_1: mv1 \neq mv2$  at the two-sided 0.05 level of significance if there is statistical evidence that both VR arms are better than control. Using the same assumptions as above and simulating 10000 trial replicates, then if both VR arms are better than the control arm, we can achieve 71.4% power to detect 5 units in PROMIS score between the two VR arms. This power was derived under the alternative hypothesis  $|mc - mv1| = 5$  and  $|mv1 - mv2| = 5$ . The actual type I error rate for this conditional test is 0.02.

For assessing the effect of VR on treatment response, we estimate power using a logistic regression model, accounting for all possible confounding factors as described in the protocol.

The outcome variable is treatment response (binary) and the predictor of interest is VR type, Distraction versus Skills-based. Table 1 gives the minimum odds ratio that can be detected with 80% power with the two-sided 0.05 level of significance as a function of baseline probability of positive response when a patient is treated with traditional VR and  $R^2$ , the proportion of variability in the predictor of interest (VR type) that is explained by all relevant baseline covariates in the model using data from 120 patients in the Distraction VR arm and 120 in the Skill-based VR arm. For example, data from 240 patients achieve 80% power to detect an odds ratio of 2.19 if the probability of positive response when a patient is treated with Distraction VR is 0.3 and 10% of the variability in VR type is explained by all other baseline covariates in the model. These odds ratios vary between 2.01 and 2.8 and are clinically meaningful. Therefore, we have enough power to test statistical significance of predictors of interest in the multivariable logistic regression model.

**Table 1.** Minimum detectable odds ratio as a function of the proportion of variability in VR type variable that is explained by all other relevant covariates in the model and the baseline probability of positive treatment response.

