#### *PGIC*

An exploratory endpoint is the change in disease severity as measured by the PGIC at Day 90. This secondary analysis will compare the treatment groups, separately, to the control group using a logistic regression analysis. Based on the PGIC assessment, a dichotomous scale of “Yes” or “No” will be derived. A favorable response of 5-7 on the PGIC indicates “Yes”, significant improvement occurred over the course of the study. An unfavorable response of 1-4 indicates “No”, significant improvement did not occur over the course of the study.

The percentage of patients in each treatment arm responding in the “Yes” and “No” categories will be compared to the percentage of patients in the control arm responding in the “Yes” and “No” categories via the Cochran Mantel-Haenszel test. We will analyze responder status (i.e. “Yes” vs “No” as the dependent variable) using logistic regression, with terms for study-arm and baseline PROMIS-PI.

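### The statement of adequate power for predictors of response is supported only for the VR-type contrast, in a model no analysis section specifies; the planned interaction tests have no power statement.

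*Protocol*

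**What the plan says.** Protocol 9.2 (Power Estimation) describes a logistic regression: "The outcome variable in treatment response (binary) and the predictor of interest is VR type, traditional versus enhanced". Table 1 lists the smallest odds ratio that "can be detected with 80% power with the two-sided 0.05 level of significance", by baseline response probability and by the share of variability in VR type explained by covariates. The section concludes: "Therefore, we have enough power to test statistical significance of predictors of interest in the multivariable logistic regression model". SAP 3.5.1 renames the contrast Distraction versus Skills-based, reprints the table, and likewise says "we have enough power to test statistical significance of predictors of interest in the multivariable logistic regression model".

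For which patients respond, Protocol 9.4.7 says "An MMRM model will be used to test for treatment by subgroup interactions". Interactions below the 10% level are flagged for further assessment, and SAP 4.6.3 (Subgroup Analyses) matches this. The protocol lists 16 subgroup headings and the SAP 10.

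The SAP specifies one logistic model of response, for PGIC at Day 90 (scores 5-7 versus 1-4), each VR arm against sham, "using logistic regression, with terms for study-arm and baseline PROMIS-PI". Protocol 9.4.9 adds a Skills versus Distraction comparison on PGIC, made only if Skills differs significantly from sham.

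**The concern.** The closing sentence speaks of predictors in the plural, but the calculation has one predictor, and it is the randomised arm. Nothing in Table 1 bears on age, comorbidity, immersive tendency or any other patient characteristic.

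Nor can the model be found. Protocol 9.2 takes its confounders from an Aim 1; the only numbered Aim 1s are in the appendices, on recruitment materials, on enrolment and completion, and on cultural barriers. SAP 3.5.1 refers to the protocol for the confounders, and the protocol does not list them. Treatment response is not defined for this model in either document.

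Protocol 2.2 asks whether patient characteristics predict response and says the study will seek to answer this. The tests that address it have a different outcome, model and predictor from the calculation. A reader of 9.2 could take those tests to be adequately powered and read null interactions as showing that patient characteristics do not matter.

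**Working it through.** **1. The plan's own figure.** The worked example is "data from 240 patients achieve 80% power to detect an odds ratio of 2.19", with the probability of response when "treated with traditional VR is 0.3 and 10% of the variability in VR type is explained". Inputs: p1 = 0.3, R² = 0.1, N = 240, two-sided 0.05.

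- Effective size per arm: 120 × (1 − 0.1) = 108.
- Odds at OR 2.19: (0.3/0.7) × 2.19 = 0.939, so p2 = 0.484 and the mean p = 0.392.
- z = [(0.484 − 0.300) × √108 − 1.96 × √(2 × 0.392 × 0.608)] / √(0.3 × 0.7 + 0.484 × 0.516) = 0.83, giving power 79.6%. The detectable OR at 80% is 2.20.

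The figure reproduces, as do 11 of the 12 cells to within 0.01. The exception is p1 = 0.5 with R² = 0: stated 2.01, recomputed 2.10 (power 75.4% at 2.01). That cell is the lower end of the range quoted in the text.

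So the table is essentially sound for what it computes: the effect of VR type on a binary response.

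**2. The tests that are planned.** Inputs from Protocol 9.2: 120 per arm, SD 10 at one visit, SD 14.14 for unadjusted change (correlation 0), and 5 points as the clinically meaningful between-arm effect. From 9.4.7: level 0.10. Assumptions, since the documents give no values: one VR arm versus sham, a binary subgroup with share f in each arm, a single-visit Day 30 contrast, and a difference in effect of 5 points.

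- SE = SD × √(2/(n f) + 2/(n(1 − f))). For f = 0.5 this is 2 × SD × √(2/n).
- Power = Φ(5/SE − 1.645).

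| Case | SD 14.14 | SD 10 |
|---|---|---|
| Even split, n = 120: SE | 3.65 | 2.58 |
| Even split, n = 120: power | 39% | 61% |
| 20:80 split, n = 120: power | 29% | 46% |
| Even split, 15% missing (n = 102): power | 35% | 56% |

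For an even split with complete data, the difference detectable with 80% power is (1.645 + 0.842) × SE, which is 9.1 or 6.4 points.

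**3. Which SD applies.** The interaction model in 9.4.7 adjusts for baseline PROMIS-PI. With SD 10 at each visit, the Day 30 residual SD is 10 × √(1 − ρ²), where ρ is the baseline to Day 30 correlation, so it is at most 10. For an even split with complete data:

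- ρ = 0: SD 10, power 61%
- ρ = 0.5: SD 8.66, power 72%
- ρ = 0.7: SD 7.14, power 86%

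Power of 80% needs SE = 5/2.487 = 2.01, so SD = 7.79 and ρ of about 0.63.

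**4. Averaging over visits.** The model has no treatment-by-subgroup-by-week term, so the interaction is averaged over Days 7, 15, 21 and 30. With residual SD 10 and an assumed equal between-visit correlation r, the variance is multiplied by (1 + 3r)/4. Power is then 79% (r = 0.5) or 71% (r = 0.7).

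**The case against.** Three points on the other side have force.

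First, a reader might infer that the plan contains no logistic model of response at all. It does. The PGIC analysis uses a binary responder status, and Protocol 9.4.9 adds a conditional comparison of the two VR arms, which is the Table 1 contrast. What is missing is the confounder-adjusted version and any link between treatment response and PGIC.

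Second, a reader might infer that the documents claim adequate power for the interaction tests, or that those tests have 39-61% power. Neither is supported. Both sections define the predictor as VR type, so the plural may be loose wording. The 39% figure uses an unadjusted change SD, although the planned model adjusts for baseline; 61% is a floor only for an even split with complete data under the plan's SD of 10. Power moves in both directions from there and exceeds 80% in favourable combinations. Taking 5 points as the difference in effect is also a choice of scale, because the plan's 5 is a main effect.

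Third, the subgroup work is already labelled exploratory in the Protocol Section 3 table, significant interactions are only flagged, and SAP 6.3 keeps exploratory tests outside the gatekeeping. That null results would be misread is a risk, not a certainty.

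These points narrow the concern. They do not supply the missing model, a definition of response, or a power statement for the tests that are planned.

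**Conclusion.** The closing sentence in Protocol 9.2 and SAP 3.5.1 is not supported beyond the VR-type contrast, and the adjusted model it refers to is specified nowhere. The tests planned for patient-level predictors have no stated power. At Day 30, for one VR arm versus sham with 120 per arm, an even binary subgroup, complete data and level 0.10, a 5-point difference in effect has about 61% power at SD 10 and 39% at SD 14.14. These are conditional illustrations. Subgroup shares, baseline correlation, between-visit correlation and dropout are not given, so the documents establish neither adequate nor inadequate power in general. The primary comparison and the sample size are not touched. The 2.01 cell in Table 1 is a separate, minor error.

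**What to change.** In both documents:

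- Delete the closing sentence on adequate power, or limit it to the VR-type contrast.
- Tie Table 1 to the PGIC comparison of Skills with Distraction, stating that treatment response means PGIC 5-7, that the comparison is conditional, and which covariates enter; otherwise drop the table. If it stays, recheck the 2.01 cell (about 2.10) and the quoted range, and remove or define the reference to Aim 1.
- In Protocol 9.4.7 and SAP 4.6.3 (Subgroup Analyses), state the interaction power with its assumptions: about 61% (SD 10) and 39% (SD 14.14) for an even split, 46% and 29% for 20:80, lower with missing data, and higher with appreciable baseline correlation or averaging over visits.
- Add that a null interaction is not evidence of no effect modification.

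No new responder analysis is needed. The cost is a text change in two sections of each document and a less favourable power statement; trial conduct and data collection do not change.
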